5.5 Subject Withdrawal and Discontinuation

Each subject meeting all general and screening eligibility criteria shall remain in the clinical investigation until completion of the required follow-up period; however, a subject's participation in any clinical investigation is voluntary and the subject has the right to withdraw at any time without penalty or loss of benefit. Conceivable reasons for discontinuation may include, but are not limited to, the following:

- Subject death
- Subject voluntary withdrawal
- Subject lost-to-follow-up
- Subject's follow-up is terminated according to Section 3.3
- Unsuccessful Implant
- LP explanted and not re-implanted
- LP abandoned and Aveir LP not re-implanted

Sites must notify the Sponsor of the reason(s) for subject discontinuation. Investigators must also report this to their respective IRB/EC as defined by their institution's procedure(s).

No additional follow-up is required or data recorded from subjects once withdrawn from the clinical investigation, except for the status (deceased/alive).

However, if a subject withdraws from the investigation due to problems related to the safety or performance of the device under investigation, the investigator shall ask for the subject's permission to follow his/her status/condition outside of the clinical investigation according to standard of care.

Lost-to-Follow-up

Clinical Investigation Plan for Europe

If the subject misses two consecutive scheduled follow-up time points and the attempts at contacting the subject detailed below are unsuccessful, then the subject is considered lost-to-follow-up. Site personnel shall make all reasonable efforts to locate and communicate with the subject (and document these efforts in the source documents), including the following, at each contact time point:

- A minimum of two telephone calls on different days over the specified follow-up windows to contact the subject should be recorded in the source documentation, including date, time and initials of site personnel trying to make contact.
- If these attempts are unsuccessful, the site should send a certified letter to the subject.
- If a subject misses one or more non-consecutive follow-up contact time points, it will be considered a missed visit. The subject may then return for subsequent visits. If the subject misses two consecutive time points and the above-mentioned attempts at communicating with the subject are unsuccessful, the subject will be considered lost-to-follow-up.

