6.4 System Revision without a Replacement Aveir LP

In the event an Aveir LP must be replaced during the follow-up period, investigators may opt to revise the Aveir LP without a replacement Aveir LP in one of the following ways:

- Retrieve the Aveir LP and implant a commercially available pacemaker, CRT device, ICD, or not opt for a replacement device.
- Deactivate the Aveir LP and implant a commercially available pacemaker, CRT device, ICD, or not opt for a replacement device.

Clinical Investigation Plan for Europe

When considering Aveir LP retrieval, investigators will refer to the respective IFUs. Sponsor representatives may also assist the team in equipment setup prior to and during a procedure.

If the subject has all Aveir LPs removed or deactivated at any time during the clinical investigation, and the subject will not receive a replacement Aveir LP, the site will follow the subject for at least 30 days. At the end of the 30 days, the investigator will withdraw the subject. If the subject has at least one active Aveir LP after a system revision procedure, the subject must continue with his/her ongoing follow-up schedule.

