8.2.2 Primary Effectiveness Endpoint #1 Analyses

The primary effectiveness endpoint #1 evaluates the 12-month composite success rate (Rate_{EP}) of acceptable atrial pacing thresholds and P-wave amplitudes in *de novo* subjects.

Parameter	Acceptable values
Pacing voltage	Pacing threshold ≤ 3.0 V at 0.4 ms
P-wave sensitivity	P-wave amplitude ≥ 1.0 mV

The primary effectiveness endpoint #1 hypothesis is:

$$H_0: \text{Rate}_{EP} \leq 80\% \quad \text{vs.} \quad H_1: \text{Rate}_{EP} > 80\%$$

where 80% is the PG

The Rate_{EP} is the proportion of subjects who have met success criteria in the primary effectiveness endpoint #1.

Success Criteria: A subject will meet the primary effectiveness endpoint #1 endpoint if: pacing threshold voltage ≤ 3.0 V at 0.4 ms at the 12-month visit **and** the sensed P-wave amplitude is ≥ 1.0 mV at the 12-month visit.

The Rate_{EP} will be estimated as a binomial proportion and the 97.5% LCB of the Rate_{EP} will be calculated using the normal approximation. The null hypothesis is rejected at the 2.5%

Clinical Investigation Plan for Europe

significance level if the LCB exceeds the PG of 80%. The p-value for the one-sided Z-test will be calculated and compared to the 2.5% significance level.

The Sponsor will analyze the primary effectiveness endpoint #1 on both the full analysis (primary analysis) and implanted populations. In the full analysis population, subjects with unsuccessful implants due to reasons other than atrial pacing/sensing (e.g. cardiac anatomy) will be excluded from the analysis. Subjects who don't meet pacing/sensing success criteria at 12 months or subjects with unsuccessful implant solely due to unacceptable atrial LP pacing or sensing will be counted as failures. Additionally, for subjects with missing 12-month pacing threshold or P-wave amplitude data, a multiple imputation analysis will be used to impute the missing outcomes.

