associated with each pacing stimulus. The pacing stimulus may stimulate the diaphragm either directly or indirectly via the phrenic nerve.

Dislodgement: The LP separates from the endocardium after the implant procedure has been completed.

Elevated Pacing Thresholds (RV): Pacing thresholds > 2.5 V at 0.4 ms at implant. Following lead maturation at 6-8 weeks, an increase in pacing thresholds of 1.2 V at 0.4 ms or greater between visits. This definition is intended to serve as a guideline and it is understood that individual subjects may have unique situations.

Elevated Pacing Thresholds (RA): Atrial pacing thresholds > 4.0 V at 0.4ms on or after the pre-discharge assessment, or if there is an increase in atrial pacing thresholds of 1.2V at 0.4 ms or greater between visits. This definition is intended to serve as a guideline and it is understood that individual subjects may have unique situations.

Established i2i Communication: A situation at the end of an implant procedure where non-zero i2i throughput in either LP transmission direction (i.e. A2V or V2A) has been demonstrated. If any of the following situations occur, i2i communication will NOT be considered established:

- a) Implanter decides to retrieve 1 or 2 LPs and not replace them exclusively due to unacceptable i2i communication; OR
- b) Implanter deliberately programs the LPs to a non-dual chamber pacing mode due to unacceptable i2i communication; OR
- c) There is zero i2i throughput in both LP transmission directions (i.e. atrial LP to ventricular LP AND ventricular LP to atrial LP)

Intermittent or loss of i2i communication: When the subject either (a) has their Aveir DR system programmed to a non-dual chamber pacing mode at the end of any pre-discharge or follow-up visit solely due to unsatisfactory i2i communication even in the absence of untoward clinical signs, or (b) undergoes a system revision intervention due to unsatisfactory i2i communication.

Implant procedure duration: Defined as the time from delivery catheter and LP insertion to removal.

Implant success rate: Defined as the number of *de novo* subjects leaving the implant procedure with both implanted and functioning LP devices, divided by the number of subjects in whom implantation is attempted.

Inadequate Fixation: When an LP separates from the endocardium after being released from the Delivery Catheter during the implant procedure.

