Sponsor understands that the following items meet the definition of serious adverse event if they require hospitalization or prolong hospitalization, even though an invasive approach may not be necessary to resolve: AV fistula, pseudoaneurysm, blood transfusions, tricuspid valve damage, pericardial effusion, pulmonary embolus, device dislodgement, right ventricular or right atrial perforation, thrombus formation on the device, ventricular arrhythmias even if not associated with an invasive strategy to remedy.

Non-invasive means such as device re-programming do not meet the criteria for medical or surgical intervention.

Successful Implant: A subject who leaves an attempted *de novo* implant procedure with functioning atrial and ventricular LPs implanted, including established i2i communication

Clinical Investigation Plan for Europe

Successful Upgrade: A subject with a pre-existing Aveir ventricular LP who was successfully implanted with an Aveir atrial LP, and the Aveir VR LP can be programmed to a dual-chamber mode

Time to discharge: Defined as the time from introducer sheath removal to discharge.

Unanticipated (serious) adverse device effect (UADE/USADE): Any serious adverse effect on health or safety or any life-threatening problem or death caused by, or associated with, a device, if that effect, problem, or death was not previously identified in nature, severity, or degree of incidence in the investigational plan or application (including a supplementary plan or application), or any other unanticipated serious problem associated with a device that relates to the rights, safety, or welfare of subjects. [21 CFR 812.3(s)]

Unavoidable adverse event: An unavoidable AE is defined as an adverse event related to the implant procedure that is expected to occur for a projected duration in all subjects.

Undersensing: The failure of the pulse generator to sense R-waves, causing delivery of inappropriately timed, asynchronous or competitive output pulses. Undersensing can sometimes be corrected by programming the device to a more sensitive setting, i.e., decreasing the millivolt value.

Unsuccessful Implant: A subject who leaves an attempted *de novo* implant procedure without a functioning atrial or ventricular LP implanted, or where i2i communication was not established.

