The primary analysis for the primary effectiveness endpoint #1 will be based on subjects in the full analysis population. Subjects with unsuccessful implants due to reasons other than atrial pacing/sensing (e.g. cardiac anatomy) will be excluded from the analysis. Subjects who don't meet pacing/sensing success criteria at 12-months or subjects with unsuccessful implant solely due to inadequate atrial LP pacing or sensing will be counted as failures. Additionally, subjects with missing 12-month pacing threshold or P-wave amplitude data, multiple imputation will be used to impute success or failure.

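### Endpoint #1: an atrial LP lost after a successful implant for pacing or sensing failure has no stated score, and on the most natural reading can be imputed as a success

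*SAP*

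**What the plan says.** SAP 2.3.2 and Protocol 8.2.2 test the 12-month composite success rate (Rate_EP) against 80%. The test passes if the 97.5% lower confidence bound (LCB), by the normal approximation, exceeds 80%. A subject succeeds if the atrial threshold and P-wave are both in range at the 12-month visit.

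The visible scoring rules are:

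- **Failure:** criteria not met at 12 months. In addition, "subjects with unsuccessful implant solely due to unacceptable atrial LP pacing or sensing will be counted as failures" (Protocol 8.2.2; SAP 2.3.2 is equivalent).
- **Excluded:** implants unsuccessful for other reasons, with cardiac anatomy as the example. SAP 2.3.2 also excludes subjects for whom neither value can be obtained because of atrial arrhythmia, other rhythm conditions or procedures.
- **Imputed:** in the SAP, "subjects with missing 12-month pacing threshold or P-wave amplitude data, multiple imputation will be used to impute success or failure"; in the Protocol, "for subjects with missing 12-month pacing threshold or P-wave amplitude data, a multiple imputation analysis will be used to impute the missing outcomes".

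Protocol Appendix II judges an unsuccessful implant as the subject leaves the "implant procedure without a functioning atrial or ventricular LP implanted, or where i2i communication was not established". It defines dislodgement as a later event: "The LP separates from the endocardium after the implant procedure has been completed". Protocol 5.5 lists "LP explanted and not re-implanted" as a reason for discontinuation separate from an unsuccessful implant.

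Protocol 6.4 allows an LP to be retrieved or deactivated without an Aveir replacement. If no active Aveir LP remains, the subject is followed for at least 30 days, and then: "At the end of the 30 days, the investigator will withdraw the subject". If one remains active, scheduled follow-up continues. Protocol 5.5 adds "No additional follow-up is required or data recorded from subjects once withdrawn from the clinical investigation", apart from vital status.

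**The concern.** Protocol 4.1.2.1 says endpoint #1 measures whether the atrial LP can pace and sense as intended. Protocol 1.1.2 uses it for both the DDD(R) and the AAI(R) indications. An atrial LP taken out of service because it stopped capturing or sensing is direct evidence against that claim; its 12-month result is not unknown in the ordinary sense.

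The visible rule nevertheless looks only at whether the value is missing. If the imputation model borrows the success rate of subjects who kept a working device, most such losses become successes. The same fault at implant would be a failure, so the score depends on when the fault appeared. The bias favours passing, in a single-arm, unblinded study judged against a fixed goal.

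**Working it through.** **1. Does the case arise, and where does it fall?**

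| Situation | 12-month atrial value | Visible rule |
|---|---|---|
| Implant unsuccessful solely for atrial pacing/sensing | none | failure |
| Implant unsuccessful for inadequate fixation | none | excluded (not solely pacing/sensing) |
| Atrial LP later lost or deactivated for pacing/sensing, not replaced | none | none specific; imputation most natural |
| Atrial LP later dislodged, not replaced | none | none specific; imputation most natural |
| Atrial LP replaced | measurable on the new LP (Protocol 6.3) | subject's value at 12 months |

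Rows 3 and 4 occur under Protocol 6.4 whether the subject is withdrawn or continues with the ventricular LP alone. SAP 2.8 treats discontinuation before 12 months as missing data and, in its visible text, only summarizes the reasons.

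**2. Inputs.** Goal 80%, one-sided 2.5%, normal approximation (SAP 2.3.2); 240 evaluable subjects (Protocol 8.3). The assumed success rate and power are blacked out, so the power behind 240 cannot be reproduced. No loss rate or imputation model is visible; both are assumed below.

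**3. Pass boundary at N = 240.** LCB = p − 1.96·√(p(1−p)/N).

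- 203/240 = 84.58%: LCB 80.01%, pass.
- 202/240 = 84.17%: LCB 79.5%, fail.

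At a true rate of exactly 80%, the exact binomial probability of 203 or more successes is 4.19%. This is the size of the rule before any loss.

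**4. One example.** Five atrial LPs are lost, and 202 of the other 235 subjects succeed.

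- Counted as failures: 202/240, LCB 79.5%, fail.
- Imputed at the observed rate, which carries about the information of 235 measured subjects: 202/235 = 85.96%, LCB 81.5%, pass.

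**5. False-pass probability.** Let q be the loss rate, and fix the true rate with losses counted as failures at 80%. Success among retained subjects is then 0.80/(1−q): 80.8, 81.6 and 82.5% for q = 1, 2 and 3%. Simulated, N = 240:

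| Treatment of losses | q = 1% | q = 2% | q = 3% |
|---|---|---|---|
| Counted as failures | about 4.2% | about 4.2% | about 4.2% |
| Imputed at half the observed rate | 4.7% | 6.2% | 8.3% |
| Imputed at the observed rate | 6.6% | 11.7% | 19.1% |

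The half-rate row stands for a model that uses poor earlier readings. Excluding the losses gives the same figures as the last row.

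**6. Chance of passing above the goal.** Exact binomial, N = 240. The minimum pass when losses are imputed at the observed rate is 199/235 (5 losses) or 195/230 (10 losses); when they count as failures it is 203 in both cases.

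| Losses | True success among retained | Imputed | Counted as failures |
|---|---|---|---|
| 5 | 90% | 99.6% | 97.1% |
| 10 | 88% | 94% | 50% |
| 10 | 90% | 99.5% | 84% |
| 10 | 92% | 100% | 98% |

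**The case against.** Several points on the other side have force.

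*The text does not clearly commit to imputation.* A subject with no working atrial LP could be said not to meet the criteria at 12 months, hence a failure. The SAP 2.3.2 exclusion for procedures that prevent measurement could be stretched to cover removal. This stands: three treatments are arguable. But they give different results, and nothing visible chooses between them.

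*Blacked-out text may hold the rule.* Parts of SAP 2.8, other SAP sections and the imputation model are not visible. This also stands, so the point concerns the visible rule only.

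*There are safeguards.* Complete-case and tipping-point analyses are planned for this endpoint, and losses that are device- or procedure-related serious events count in the safety endpoints. These make the handling more visible, but do not set the primary Rate_EP decision.

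Three stronger readings are tempting and are not supported:

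- A reader might infer that dislodgement is also scored as a failure at implant and only later imputed. Appendix II confines dislodgement to the period after the procedure. Its implant-stage counterpart is inadequate fixation, and an implant unsuccessful for that reason would be excluded. Only the scoring gap applies to dislodgement.
- A reader might infer that a replaced atrial LP must count as a failure. SAP 2.3.2 scores the subject at the 12-month visit, and Protocol 6.3 keeps such subjects on schedule, so scoring the original device is a preference.
- A reader might infer that the false-pass figures forecast this trial. They need an assumed loss rate, a true rate of exactly 80% and a particular imputation model.

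**Conclusion.** The concern holds for atrial LPs lost or deactivated without replacement, after a successful implant, because of pacing or sensing failure. On the most natural reading of the visible text such a subject can be imputed as a success, which is inconsistent with the implant-stage rule. For unreplaced dislodged LPs the scoring is equally unstated, but there is no such inconsistency.

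The effect matters when the result is near the goal or losses are more than a few. False-pass inflation from 4.2% to about 7, 12 and 19% at 1, 2 and 3% loss is at the unfavourable end, because it assumes imputation at the observed rate; imputation at half that rate gives about 5, 6 and 8%. With five losses and 90% success among retained subjects, the chance of passing barely moves. The point should be fixed because the rule sets a primary decision and is cheap to state. Confidence is moderate, given the blacked-out text and the competing readings.

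**What to change.** In SAP 2.3.2 and Protocol 8.2.2:

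1. Count as an endpoint #1 failure any subject whose atrial LP was lost or deactivated without replacement before the 12-month measurement because of atrial pacing failure, sensing failure or dislodgement. Including dislodgement goes beyond the present implant rule, so state it explicitly.
2. Limit multiple imputation to values missing for unrelated reasons.
3. State that the exclusion for procedures in SAP 2.3.2 does not cover device loss.
4. For replaced atrial LPs, keep the subject-level 12-month value as primary, and add a sensitivity analysis that scores the original LP as a failure.

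If blacked-out text already contains such a rule, state it in SAP 2.3.2.

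The cost is a short scoring rule and no added visits. The reason for revision must be recorded: a System Revision Form exists, but its content is not shown, so a field may be needed. The observed success rate may be slightly lower.

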2.3.3 Primary Effectiveness Endpoint #2 Analysis

The primary effectiveness endpoint #2 evaluates the 3-month AV synchrony success rate ($Rate_{AV}$) at rest while sitting using a Holter monitor in-clinic.

AV synchrony success is defined as subjects with a paced or sensed ventricular beat within 300 ms following a paced or sensed atrial beat for at least 70% of evaluable cardiac cycles.

The primary effectiveness endpoint #2 hypothesis is:

$$H_0: Rate_{AV} \leq 83\% \quad \text{vs.} \quad H_1: Rate_{AV} > 83\%$$

where 83% is the performance goal. The $Rate_{AV}$ is the proportion of subjects who met success criteria in the primary effectiveness endpoint #2.

The $Rate_{AV}$ will be estimated as a binomial proportion and the 97.5% LCB of the $Rate_{AV}$ will be calculated using the normal approximation. The null hypothesis is rejected at the 2.5% significance level if the LCB exceeds the PG of 83%. The p-value for the one-sided Z-test will be calculated and compared to the 2.5% significance level.

The primary analysis for the primary effectiveness endpoint #2 will be based on subjects in the full analysis population. Subjects with unsuccessful implant solely due to a failure to establish i2i communication at end of implant procedure will be included and imputed as failures. Subjects with unsuccessful implants due to reasons other than AV synchrony (e.g., cardiac anatomy) will be excluded from this analysis.

Statistical Analysis Plan

Additionally, among the implanted population only the AV synchrony data available for evaluation will be used.

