6.6.1.1 Data submission

The site will complete and submit the following case report forms and device print outs to Abbott Medical using the EDC system:

- Follow-up Visit Form (includes medication changes)
- Aveir LP Assessment and Programming Form (Follow-Up) with device session print out PDFs
- Quality of Life Assessment (EQ-5D 5L)
- 6 Minute Walk Test Form, if applicable
- Adverse Event Form, if applicable
- Device Deficiency Form, if applicable
- Deviation Form, if applicable
- Device Accountability Log, if applicable
- System Revision Form, if applicable
- Healthcare Utilization Form, if applicable
- COVID-19 Assessment Log, if applicable
- Study Withdrawal Form, if applicable

All source documentation associated with the 6MWT, including device session printouts, source worksheets, and LP data files should be de-identified and submitted to the Sponsor.

² Administration of the 6MWT can be done any time between the 1-month and 3-month follow-up visit until 30 subjects contribute to the analysis. Subjects

Clinical Investigation Plan for Europe

6.6.2 3-Month Follow-Up Visit

The 3-month follow-up visit will occur 90 days (± 30 days) post-implant procedure and will include the following assessments:

- Assess for adverse events and deviations from investigation plan
- Assess for changes in beta blockers, ACE, ARB, anti-coagulants, anti-platelets, anti-arrhythmics
- Assess Quality of Life (EQ-5D 5L)
- Measure and record LP performance, as described in Section 6.2.5 LP Assessment and Programming
- Measure and perform in-clinic AV Synchrony Assessment only for *de novo* subjects programmed in a dual-chamber pacing mode as described in Section 6.6.2.1
- Program Aveir LP and adjust programmable parameters of LP, as needed
- **Optional:** CAEP Protocol only for those capable *de novo* subjects who may be appropriately programmed temporarily in AAIR pacing mode and who have a tolerance of high sensor-driven rates³
 - If the 6MWT is conducted the same day as the CAEP protocol, wait at least 1 hour after the 6MWT has been completed prior to starting the CAEP protocol.
 - The optimized sensor parameters resulting from the 6MWT are advised for the CAEP protocol, however, the physician has discretion to alter these parameters. Administer the CAEP protocol with rate-response feature in **AAIR ON** mode (refer to the CAEP protocol in Appendix V).
 - After completing the CAEP protocol, program Aveir LP and adjust programmable parameters of the LP, as needed.

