6.6.2.1 AV Synchrony Assessment – In-Clinic

Subject Population

All *de novo* subjects who can be programmed to a dual chamber pacing mode will be administered the in-clinic AV Synchrony Assessment.

Setup

³ Administration of the CAEP protocol can be done any time between the 3- month and 6-month follow-up visit until 30 subjects contribute to the analysis

⁴ Holter data collection can be done any time between the 3- month and 6-month follow-up visit.

Clinical Investigation Plan for Europe

After the 3-month LP Assessment and Programming is performed and device session printouts obtained, the site will clear the device diagnostics prior to starting the in-clinic AV Synchrony Assessment.

A Holter monitor will be setup and worn by the subject according to the instructions provided by the Sponsor and/or Core Lab. The setup may include adjusting the clock times on the Holter Monitor or Merlin Programmer so that the beginning and end of each position/activity can be identified on both devices.

The subject will also be connected to the Merlin Programmer at certain periods during the assessment. The investigator may also need to reprogram the base rate to improve the likelihood of atrial pacing for select patients. LP interrogation and Holter recording should not take place simultaneously to minimize device artifacts or noise on the Holter.

The site will be trained to properly set up the Holter and Merlin Programmer for the in-clinic AV Synchrony Assessment through separate instructional materials.

AV Synchrony Assessment For Primary Effectiveness Endpoint #2:

While wearing the Holter monitor, the subject should remain in a seated position at rest for 5 minutes while the Holter will record the subject's cardiac rhythm. The site will record the Holter start and stop recording times on the AV Synchrony Assessment CRF and then interrogate the LP. At the end of the assessment period, the site will obtain a device session printout. The site will be trained to administer the in-clinic AV Synchrony Assessment and send the Holter data to the Core Lab for AV Synchrony analysis.

The Sponsor will evaluate the data from this assessment for the primary effectiveness endpoint #2.

Additional AV Synchrony Assessment in Various Positions/Activity Levels:

While wearing the Holter monitor, the subject's cardiac rhythm will be recorded while the subject assumes the following positions and activity levels in the following order for 2 minutes each:

- Supine
- Left Lateral

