6.7 Schedule of Events

CIP Activity	Screening/ Enrollment	Baseline	Implant Procedure	Pre-Discharge (0-2 days)	1 Month (±15 days)	3 Month (±30 days)	6 Month (±30 days)	12 Month and Every 6 months until study completion (±45 days)
Eligibility Criteria	X							
Informed Consent Process	X							
Screening Log	X							
Pregnancy Test		X†						
Demographics and Medical History		X						
RA Characterization Imaging		Y	Y					
Changes in Medication			X	X	X	X	X	X
12-lead ECG		X		X				
Cine of Final LP Placement			X					
Chest X-ray of LP				X				
Aveir Assessment and Programming			X	X	X	X	X	X
In-clinic Holter AV Synchrony Protocol						X*		
Sensor optimization exercise test 6MWT					X**	X**		
Graded exercise test CAEP Protocol						X**	X**	
24 hour Holter monitor with patient diary						X**	X**	

Clinical Investigation Plan for Europe

CIP Activity	Screening/ Enrollment	Baseline	Implant Procedure	Pre- Discharge (0-2 days)	1 Month (±15 days)	3 Month (±30 days)	6 Month (±30 days)	12 Month and Every 6 months until study completion (±45 days)
EQ-5D 5L patient survey		X			X	X	X	X***
Device Accountability Log			X	(X)	(X)	(X)	(X)	(X)
Adverse Event		(X)	(X)	(X)	(X)	(X)	(X)	(X)
Deviation		(X)	(X)	(X)	(X)	(X)	(X)	(X)
Device Deficiency			(X)	(X)	(X)	(X)	(X)	(X)
System Revision				(X)	(X)	(X)	(X)	(X)
Withdrawal		(X)	(X)	(X)	(X)	(X)	(X)	(X)
COVID-19 Assessment log		(X)	(X)	(X)	(X)	(X)	(X)	(X)
Healthcare Utilization			(X)	(X)	(X)	(X)	(X)	(X)

X = Required for all subjects

X[†] = For female subjects of childbearing age

X* = For *de novo* subjects only

X** = For select appropriate *de novo* subjects only. CIP activity only needs to be done once among designated visits.

X*** = EQ-5D 5L patient survey required at 12-month visit only

(X) = If applicable for all subjects

Y = Optional, if available. Imaging at baseline visit applies to pre-existing subject imaging only (e.g. MRI, CT).

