8.2.3 Primary Effectiveness Endpoint #2 Analyses

The primary effectiveness endpoint #2 evaluates the 3-month AV synchrony success rate ($Rate_{AV}$) at rest/seated using a Holter monitor in-clinic. AV synchrony success is defined as subjects with a paced or sensed ventricular beat within 300 ms following a paced or sensed atrial beat for at least 70% of evaluable cardiac cycles. The primary effectiveness endpoint #2 hypothesis is:

$$H_0: Rate_{AV} \leq 83\% \text{ vs. } H_1: Rate_{AV} > 83\% \\ \text{where } 83\% \text{ is the PG}$$

The $Rate_{AV}$ is the proportion of subjects who have met success criteria in the primary effectiveness endpoint #2.

The $Rate_{AV}$ will be estimated as a binomial proportion and the 97.5% LCB of the $Rate_{AV}$ will be calculated using the normal approximation. The null hypothesis is rejected at the 2.5% significance level if the LCB exceeds the PG of 83%. The p-value for the one-sided Z-test will be calculated and compared to the 2.5% significance level.

The Sponsor will analyze primary effectiveness endpoint #2 on the full analysis (primary analysis) population. In the primary analysis, subjects who don't meet AV synchrony success criteria at 3 months or subjects with an unsuccessful implant solely due to a failure to establish i2i communication at the end of implant procedure will be imputed as endpoint failures. Subjects with unsuccessful implants due to reasons other than AV synchrony (e.g., cardiac anatomy) will be excluded from the analysis.

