8.7 Procedures for Accounting for Missing Data

Every effort will be made to collect all required data. All available safety and effectiveness data will be used in the analysis. Sensitivity analysis will be performed to evaluate the potential impact of the missing data on the primary safety and effectiveness endpoints. The details of missing data handling will be described in the Statistical Analysis Plan.

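### Primary effectiveness endpoint #2 has no failure rule for implanted subjects who lose dual-chamber function before month 3, so device failures can leave the denominator

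*SAP*

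**What the plan says.** SAP 2.3.3 tests the month-3 AV synchrony rate against 83% in the full analysis population, using a normal-approximation 97.5% lower bound. Among subjects with no result it sorts two groups. An unsuccessful implant solely because i2i was not established at the end of the procedure is a failure; an unsuccessful implant for another reason is excluded. For everyone else the only text is: "Additionally, among the implanted population only the AV synchrony data available for evaluation will be used".

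Protocol 8.2.3 counts as failures "subjects who don't meet AV synchrony success criteria at 3 months or subjects with an unsuccessful implant solely due to a failure" to establish i2i at implant. It does not say whether an implanted subject who was never tested has not met the criteria. Protocol 8.7 adds: "All available safety and effectiveness data will be used in the analysis".

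The protocol makes three statements on who is tested at month 3:

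- Section 6.6.2: de novo "subjects programmed in a dual-chamber pacing mode as described in Section 6.6.2.1".
- Section 6.6.2.1: de novo "subjects who can be programmed to a dual chamber pacing mode will be administered the in-clinic AV Synchrony Assessment".
- Section 6.7: the row "In-clinic Holter AV Synchrony Protocol" is marked for de novo subjects, with no limit on mode.

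Protocol 6.4 covers revision without a replacement device. A subject left with one working device stays in the study: "If the subject has at least one active Aveir LP after a system revision procedure, the subject must continue with his/her ongoing follow-up schedule". If all devices are removed or deactivated, "the site will follow the subject for at least 30 days. At the end of the 30 days, the investigator will withdraw the subject".

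**The concern.** The same loss of function is treated differently according to when it happens. No i2i link at the end of the implant is a failure. A link lost a month later, leading to revision or a mode change, may produce no month-3 result and so no entry in the denominator. Endpoint #1 does give a primary-analysis rule for missing results, multiple imputation (SAP 2.3.2). Endpoint #2 gives no equivalent.

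This missingness is related to the outcome. Under protocol 2.2.3.1, a sustained i2i disruption makes the system revert to ventricular-only pacing, so subjects who lose the link may well have poor AV synchrony. Leaving them out would then raise the rate that is compared with 83%. A mode change alone would not reliably appear elsewhere: Appendix II says re-programming does not meet the intervention criterion for a serious adverse event.

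**Working it through.** **1. Who can go untested.**

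- *One active device after revision (6.4).* The subject stays in follow-up but cannot be in a dual-chamber mode, so is not testable under 6.6.2 or 6.6.2.1. This is the clearest case.
- *All devices removed or deactivated (6.4).* The subject is withdrawn after at least 30 days, possibly before the month-3 window (90 ± 30 days, i.e. day 60–120).
- *Taken out of dual-chamber mode for unsatisfactory i2i* (defined in Appendix II; 6.2.4 permits mode changes at any time). The subject is untested under the 6.6.2 wording, but may be tested under 6.6.2.1.
- *Not affected:* subjects given a replacement device (6.3), subjects still in dual-chamber mode with poor i2i (they are tested and can fail), and subjects switched at the end of the month-3 visit after testing.

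**2. Which reading of the SAP.** SAP 2.8 varies the success rate among subjects with missing endpoint #2 data and lists the i2i-at-implant failures separately. If every untested subject were already a failure, there would be nothing to vary. Together with protocol 8.7 this points to available-case handling, without proving it.

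**3. Inputs.** Goal 0.83 and the Wald rule are from SAP 2.3.3; n = 267 evaluable is from SAP 2.4 and protocol 8.3. The assumed rate and power behind 267 are redacted, so that figure cannot be reproduced. The gap 300 − 267 = 33 (33/300 = 11%) looks like a non-evaluable allowance, but this is an inference.

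**4. Cut-off.** LCB = p − 1.96·√(p(1−p)/n).

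- 233/267 = 87.3%: LCB 0.8327, pass.
- 232/267 = 86.9%: LCB 0.8284, fail.
- 233/268 (one dropped failure restored): LCB 0.8291, fail.

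**5. Dropped subjects m needed to reverse a pass.** If all m would have failed, find the smallest m with LCB(x, 267 + m) ≤ 0.83:

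| Observed | m | Restored | LCB | m/(267+m) |
|---|---|---|---|---|
| 235/267 (88%) | 4 | 235/271 | 0.8267 | 1.5% |
| 240/267 (90%) | 9 | 240/276 | 0.8298 | 3.3% |
| 246/267 (92%) | 16 | 246/283 | 0.82998 | 5.7% |
| 254/267 (95%) | 26 | 254/293 | 0.8280 | 8.9% |
| 259/267 (97%) | 32 | 259/299 | 0.8276 | 10.7% |

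If half would have failed (even m only):

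| Observed | m | Restored | LCB | m/(267+m) |
|---|---|---|---|---|
| 235/267 (88%) | 8 | 239/275 | 0.8292 | 2.9% |
| 240/267 (90%) | 22 | 251/289 | 0.8296 | 7.6% |
| 246/267 (92%) | 40 | 266/307 | 0.8284 | 13.0% |

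**6. False-pass probability when the true rate is 83%.** Let q be the share dropped and f the share of those who would have failed. The rate among tested subjects is p = (0.83 − q(1−f))/(1−q), and P(pass) = P(X ≥ 233 | 267, p), exact binomial. With q = 0 it is 3.4%; the excess over 2.5% comes from the Wald rule itself. The number dropped is 267q/(1−q).

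| q (subjects) | f = 1 | f = 0.5 | f = 0.25 |
|---|---|---|---|
| 1% (about 3) | 7.2% | 4.7% | 3.7% |
| 2% (about 5) | 13.9% | 6.3% | 4.0% |
| 3% (about 8) | 24.4% | 8.3% | 4.3% |

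Inflation of the rate is q(f − 0.17)/(1−q). At q = 3% that is 2.6, 1.0 and 0.2 points for f = 1, 0.5 and 0.25. It is zero at f = 17%, the break-even share.

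**The case against.** - **The reading is not settled.** The definition of the implanted population is not readable, and text may have been lost without a marker. In protocol 8.2.3 subjects who do not meet the month-3 criteria are said to be imputed as failures; since an observed failure needs no imputation, that could be stretched to cover untested subjects. This stands as a reason for moderate confidence, but it conflicts with the separate missing-data group in SAP 2.8, and a population definition would not by itself assign outcomes.
- **Available-case analysis with a prespecified tipping point is a recognised approach.** True, and it would expose the fragility. It does not decide pass or fail, and its readable text does not separate device-related from unrelated missingness.
- **The group is narrow.** Acute i2i problems, including non-dual-chamber programming or retrieval without replacement for i2i at the end of the implant, already count as failures. Some invasive device-related revisions may also count in the safety endpoint. This stands and limits the likely size.
- **The larger false-pass figures are hypothetical.** They need a true rate exactly at the goal and every dropped subject to be a failure. This stands. Subjects with intact AV conduction may remain synchronous, and the planning rate is redacted, so how likely an 87–90% result is cannot be judged.

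**Conclusion.** The concern holds and should be fixed; confidence is medium because the key sentence can be read two ways. On the direct reading, a primary-endpoint denominator can lose device failures. On the other, the primary analysis has no readable rule for these subjects. The effect on the conclusion is conditional. One dropped failure is enough to reverse a result exactly at the cut-off, and nine at 90% observed. At about 95% or more it takes 26 or more, and the practical effect is small. The bias favours the device only if more than 17% of those dropped would have failed (taking a true rate of 83%). These sizes rest on n = 267 and on assumed drop rates and failure shares, none of which the documents give.

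**What to change.** - In SAP 2.3.3 and protocol 8.2.3, state that in the primary analysis an implanted de novo subject counts as a failure if there is no month-3 result because of unsatisfactory i2i, or because a device was dislodged, deactivated or retrieved without replacement for a device reason.
- For missingness unrelated to the device (missed visit, unreadable Holter, unrelated death or withdrawal), keep available-case handling or use multiple imputation as for endpoint #1. Report the available-case rate as supportive.
- Say whether the sentence on available data belongs to the primary analysis.
- Reconcile protocol 6.6.2, 6.6.2.1 and 6.7 on who is tested, and protocol 8.2.3 with SAP 2.3.3.
- Use the same classification in the SAP 2.8 tipping-point analysis.
- Confirm that the case report forms record why a subject was not tested. They are under separate cover, so this cannot be checked here; if they do not, a reason field is needed.

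The cost is wording plus possibly one form field. The rate may come out slightly less favourable, and a few subjects with intact AV conduction may be counted conservatively as failures.
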